13. STUDY PROCEDURES

13.1 Subject Identification

Each subject will be assigned a unique subject number. Subject numbers will not be reassigned or reused for any reason. Only their assigned subject number, initials, and date of birth should identify subjects to the Sponsor. The investigator must maintain a list of potential subjects and enrolled subjects using the Subject Screening/Enrollment Log.

Any potential subjects who are pre-screened can be added to the log by recording their screening number and initials only. Those who sign the ICF will be assigned a unique study ID.

13.2 Subject Enrollment

Subjects who meet all inclusion and exclusion criteria will be considered eligible for enrollment. Subjects will be considered enrolled on Day 1 following final confirmation of the intra-operative inclusion/exclusion criteria. Hence, subjects who begin a surgical procedure may exit the study as a screen failure. Once enrolled, a subject may only exit the study as a withdrawal (not a screen failure). The reason for withdrawal will be documented by the investigator on the Subject Screening/Enrollment Log.

13.3 Screen Failures

Subjects who sign an informed consent form and fail to meet the inclusion and/or exclusion criteria are defined as screen failures. For all screen failures, the investigator will record the reason for the screen failure on the Subject Screening/Enrollment Log. A copy of the log will be retained in the investigator's study files.

13.4 Description of Study Procedures

Subjects enrolled will follow the study procedures outlined in Section 13.

13.4.1 Magnetic Resonance Imaging

Magnetic resonance imaging (MRI) of the rotator cuff tear will be obtained during screening (baseline). A screening MRI scan will not be required if a MRI scan was obtained within 6 months of screening based on a review of the subject's medical history. All pre-operative screening or prior qualifying scans and post-operative study scans should be performed on a 1.5T magnet or better. Additionally, a standardized imaging protocol will be utilized for all images collected as part of the study procedures.

All radiographic images will be read and reviewed by Medical Metrics Inc. to confirm inclusion criteria.

13.4.2 Veterans RAND 12-Item Health Survey (VR-12)

The VR-12 is a 12-item self-administered health survey. The VR-12 consists of eight scales which evaluate physical health and mental health.

Physical Health Scales:

- General Health
- Physical Functioning
- Role-Physical
- Bodily Pain

Mental Health Scales:

- Role-Emotional

- Vitality
- Mental Health
- Social Functioning

The responses to the physical health scales will be evaluated to produce the Physical Component Score (PCS), and the responses to the mental health scales will be evaluated to produce the Mental Component Score (MCS). Both the PCS and MCS will be determined for all subjects at screening, and at 3 months, 6 months, and 12 months postoperative.

13.4.3 ASES Rating Scale

The American Shoulder and Elbow Surgeons (ASES) Functional Questionnaire is an eleven-item self-report questionnaire consisting of ten questions which evaluate function and one question that evaluates pain. The function section of the survey yields a score between 0 and 30, with a score of zero indicating maximum disability. VAS Pain Score is included and is measured on a ten point scale, with a maximum pain score of ten. ASES Ratings will be determined for all subjects at screening, and at 3 months, 6 months, and 12 months postoperative.

13.4.4 Delivery of BioWick SureLock Implant

The approved surgical technique will be followed for delivery of the BioWick SureLock Implant. The surgical technique will be provided separately.

13.5 Procedures To Be Conducted at Each Study Site Visit

13.5.1 Screening (Day -28 to -1)

The screening period of the study will take place up to 28 days prior to enrollment. Subjects will visit the study site and receive initial study documents including the ICF. Subjects will be given ample time to review and ask any questions about the clinical trial prior to signing informed consent. Once informed consent is obtained, the subject will be screened according to inclusion and exclusion criteria.

Site personnel will evaluate the subject's current pain level using the VAS pain scale. Disability and function will be assessed through evaluation of ASES scores, VR-12 scores, and ROM measurements. These evaluations will serve as the preoperative baseline scores.

Screening Visit Tasks

- Informed consent
- Inclusion/exclusion criteria
- Assess prior medications
- Medical history
- Physical exam

- MRI exam (may be obtained from medical history within previous 6 months)
- ASES Physician and Patient Scores
- VR-12 scores
- Concomitant Medications

13.5.2 Enrollment/Visit 1 (Day 1)

Subjects who meet all pre-operative inclusion/exclusion criteria will return to the study site for their surgical procedure and enrollment into the study. Upon arrival at the site and final confirmation of the pre-operative inclusion/exclusion criteria, the subject will be prepped for the surgical procedure. Final confirmation of the inclusion/exclusion criteria will be made intra-operatively, at which point subjects will be enrolled in the study if they continue to be study-eligible.

Standard post-operative care will occur for all subjects according to site procedures. The subjects will be assessed for any adverse events that have occurred following the placement of the study device and concomitant medications will be recorded. Prior to hospital discharge, the site will go over all rehabilitation procedures with the subject per the rehabilitation protocol for the study.

Enrollment/Visit 1 Tasks

- Confirm pre-operative inclusion/exclusion criteria
- Surgical Procedure
 - Confirm intra-operative inclusion/exclusion criteria
 - Use of BioWick SureLock implant
- Assess any AEs

13.5.3 3 Months/Visit 2 (Day 90 ± 14 Days)

Upon arrival at the clinic, site personnel will evaluate the subject's current pain level using the ASES. Disability and function will be assessed through evaluation of ASES scores and VR-12 Scores. The subject will be asked about any adverse health events that have occurred since implantation of the device as well as any medications they are taking.

Visit 2 Tasks

- VAS scores
- ASES scores
- VR-12 scores
- ROM measurements
- Assess AEs
- Concomitant medications

13.5.4 6 Months/Visit 3 (Day 180 ± 30 Days)

Upon arrival at the clinic, site personnel will evaluate the subject's current pain level using the ASES. Disability and function will be assessed through evaluation of ASES scores, and VR-12 Scores. The subject will be asked about any adverse health events that have occurred since the last study visit as well as any medications they are taking.

Visit 3 Tasks

- VAS scores
- ASES scores
- VR-12 scores
- ROM measurements
- Assess AEs
- Concomitant medications

13.5.5 12 Months/Visit 4 (Day 365 ± 30 Days)

Upon arrival at the clinic, site personnel will evaluate the subject's current pain level using the ASES. Disability and function will be assessed through evaluation of ASES scores, and VR-12 Scores. The subject will be asked about any adverse health events that have occurred since implantation of the device as well as any medications they are taking.

Visit 4 Tasks

- VAS scores
- ASES scores
- VR-12 scores
- ROM measurements
- Assess AEs
- Concomitant medications
- Complete Study Completion CRF

After completion of the final procedure required for this visit, the subject's participation in the study is complete, and the site should fill out the Study Completion Case Report Form (CRF).

13.5.6 Coronavirus (COVID-19) Expectations

If subjects are not allowed at the clinic for visits or if subjects refuse to come into the clinic due to COVID-19, then the following tasks should take place:

- Subject questionnaires (VAS, ASES, and VR-12) will be mailed to the subject for completion. These questionnaires should not be completed via phone. If the site does not receive a response from the subject, the site must attempt to contact the subject

and/or re-mail the subject questionnaires at least three (3) times within the visit window before submitting a protocol deviation, unless a response is received.

- The site will attempt to contact the subject to inquire of adverse events that may have occurred and/or been resolved since their last visit. The site is required to perform at least three (3) contact attempts to obtain this information. These contact attempts must be documented in the subject's study binder. If there is no response by the end of the visit window, a note-to-file (NTF) must be added to the subject's study binder indicating new adverse events were not confirmed for the visit.
- ROM measurements will not be required; however, a protocol deviation must be submitted.
- Label protocol deviations as being related to COVID-19, as applicable

Please note that these expectations are *specifically* for COVID-19 situations. If a subject misses a visit unrelated to COVID-19, this section does not apply and a "Missed Visit" protocol deviation will be submitted.

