12.3 Subject Withdrawal

Subjects may discontinue from the study at any time. A subject may be discontinued from the study for the following medical or administrative reasons:

- **Subject Withdrawal of Consent** - Subjects will be free to discontinue from the study at any time and for any reason but must notify the study site of their exit from the study.
- **Adverse Event** – If during the procedures the subject suffers an AE that, in the judgment of the PI, Sponsor or medical monitor, presents an unacceptable consequence or risk to the subject, the subject will be discontinued from further participation in the study.
- **Lost to Follow Up** – Subjects discontinue from the study without notifying the study site.
- **Serious Protocol Violation** – If, during enrollment in the study, the subject fails to follow, violates or refuses to participate in any of the procedures described in the protocol then the subject will be discontinued from the study at the discretion of the Sponsor. If, at any point during the study, a subject is determined to have been erroneously enrolled into the study, the subject will be discontinued from the study due to protocol violation.
- **Other** - If the above reasons are not applicable, “Other” will be selected as the option and the appropriate reason for subject withdrawal provided.

For subjects who discontinue or are withdrawn from the study for any reason, the PI will notify the Sponsor and attempt to recover the following:

- AE occurrences since the last visit to the study site
- Concomitant medication usage since the last visit to the study site

If the subject is withdrawn at a study visit, the procedures for an early termination visit will be conducted to assess their continued well-being.

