16.5 Statistical and Analytical Plans

16.5.1 Primary Endpoint Analyses

Implant survivorship for each subject will be determined by whether the subject undergoes a revision or reoperation of the study device. Survivorship will be assessed using a Kaplan-

Meier analysis. Data will be considered right-censored for all patients that do not have a device failure. For patients lost-to-follow-up, their last available clinical visit will be used as the censored date. For patients that die during the study, their death date will be used as the censored date. The survivorship point estimate and 95% confidence interval about the point estimate will be calculated for the one-year primary endpoint.

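### After a 12-month visit missed for a non-COVID reason, no defined follow-up is required, and reoperation status is not named as an item to ask about

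*Combined protocol and SAP*

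**What the plan says.** Section 13.5.6 describes what a site does when COVID-19 keeps a subject away. VAS, ASES and VR-12 forms are mailed, with at least three follow-up attempts inside the visit window. Separately: "The site will attempt to contact the subject to inquire of adverse events that may have occurred and/or been resolved since their last visit". At least three attempts are required here too, and they are documented. The section then limits itself: "Please note that these expectations are *specifically* for COVID-19 situations". For other absences: "If a subject misses a visit unrelated to COVID-19, this section does not apply and a 'Missed Visit' protocol deviation will be submitted".

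Other text that bears on a missed visit:

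- Section 12.3 defines loss to follow-up as: "Subjects discontinue from the study without notifying the study site". It also sets a recovery duty: "For subjects who discontinue or are withdrawn from the study for any reason, the PI will notify the Sponsor and attempt to recover", followed by two items, concomitant medication and "AE occurrences since the last visit to the study site".
- The 6-month visit (Section 13.5.4) asks about adverse events since the previous study visit. At 12 months (Section 13.5.5) the look-back is longer: "The subject will be asked about any adverse health events that have occurred since implantation of the device".
- Section 17.4 records adverse events until the subject leaves the study, with onset and resolution dates and the action taken.
- Section 16.5.1 fixes the censoring date: "For patients lost-to-follow-up, their last available clinical visit will be used as the censored date".

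**The concern.** The primary endpoint is whether, and when, the study device was reoperated on or removed within 12 months. That can be learned by telephone or letter, so a missed clinic visit need not mean a missing primary outcome. The plan already has a remote process, but ties it to the reason for the absence. The documents give no reason for that restriction.

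The weak place is Visit 4. A subject last seen at Visit 3 who then misses Visit 4 for a non-COVID reason leaves about half of the endpoint period unobserved. If that subject is treated as lost, follow-up is censored at Visit 3. Kaplan-Meier takes such censoring to be unrelated to failure. A subject who stays away because the repair failed and was reoperated on elsewhere would break that assumption, and the plan calls for no information that would show it. The mailable questionnaire scores for the visit are lost as well, although these are secondary endpoints with descriptive summaries only.

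**Working it through.** **1. What is required after a non-COVID missed visit**

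- *3-month visit missed, subject returns:* the 6-month look-back reaches to the last attended visit and the 12-month look-back reaches to implantation. Adverse events are covered; the 3-month questionnaires are not.
- *6-month visit missed, subject returns:* the 12-month look-back covers adverse events; the 6-month questionnaires are not recovered.
- *12-month visit missed:* there is no later visit. What remains is the Section 12.3 recovery duty. It starts only once the subject counts as discontinued or withdrawn, sets no number, timing or documentation of attempts, and omits questionnaires. The early-termination assessments do not help a subject who does not attend: Section 12.3 ties them to withdrawal at a study visit, and Table 7.1 footnote 2 to a return to the clinic.

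**2. What is asked when contact is made**

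Sections 12.3 and 13.5.6 both ask about adverse events. Neither names reoperation, revision or device removal. A reoperation could surface as an adverse event or as the action taken for one. The dates that Section 17.4 lists are those of the event, which need not be the date of the reoperation.

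**3. Length of the unobserved period**

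Visit 3 is at Day 180 ± 30 (Table 7.1). A subject last seen then and not again has 365 − 180 = 185 days unobserved (185/365 = 51%). Across the Visit 3 window the range is 365 − 210 = 155 to 365 − 150 = 215 days.

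**4. The plan's own loss figure**

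Section 16.2 inflates 59 evaluable subjects for 15% loss: 59/(1 − 0.15) = 69.4, rounded up to 70, against 71 stated. That is close enough to use. With 71 enrolled, 71 − 59 = 12 losses (16.9%) can occur before the evaluable number falls below 59. The 10.7% half-width in the same section does not reproduce at n = 59 and 85% (the Wald value is 9.1%). That is a separate matter and does not affect this point.

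**5. Illustration of the stake**

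Assumptions: all of the planned loss has unknown 12-month status, and survivorship in those followed is the planned 85%. Simple proportions are used in place of Kaplan-Meier.

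- Unknown: 71 × 0.15 = 10.65, about 11. Followed: 71 − 11 = 60.
- Failures among those followed: 9, so 1 − 9/60 = 85.0%.
- None of the 11 fails: 1 − 9/71 = 87.3%.
- All of the 11 fail: 1 − 20/71 = 71.8%.
- The 11 fail at 30% (assumed): 1 − (9 + 3.3)/71 = 82.7%.
- The 11 fail at 45% (assumed): 1 − (9 + 4.95)/71 = 80.4%.

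With less loss the range narrows. At 5% loss, 4 are unknown and 10 of 67 followed subjects fail, giving 1 − 14/71 = 80.3% to 1 − 10/71 = 85.9%.

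If only 4 of the 11 losses arose from this rule and failed at 30%, with the other 7 failing at 15% (all assumed), the figure is 1 − (9 + 1.2 + 1.05)/71 = 84.2%, a shift of 0.8 points.

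**The case against.** A reader might infer from Section 13.5.6 that anyone who misses a visit for a non-COVID reason is simply lost, with no attempt to learn what happened. The documents do not support that. A missed visit is not an exit from the study, and the later look-backs pick up adverse events from a missed 3- or 6-month visit if the subject returns. Section 12.3 obliges the investigator to try to recover adverse events from every subject who discontinues, and loss to follow-up is one of its listed reasons. Section 13.5.6 requires a deviation form but does not forbid contact, and Section 17.4 makes the investigator responsible for seeing that all adverse events are reported. These objections stand, and they confine the primary-endpoint gap mainly to Visit 4.

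It is also fair to say that the COVID-19 contact asks only about adverse events, as Section 12.3 does, so extending it unchanged would not secure the primary endpoint. That stands too, and is why the fix needs an explicit question.

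The size can be challenged as well. The 15% is a general allowance that the plan does not split by cause, and some of those subjects could not be reached by any number of calls. At an assumed 30% failure rate in all 11 the shift is 2.3 points (85.0 − 82.7), well inside the stated 10.7% half-width. This limits what can be claimed about size. It does not remove the gap at Visit 4 or the loss of questionnaires.

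**Conclusion.** The concern holds in a limited form. After a non-COVID missed visit the plan requires no questionnaires and no defined contact. At the 12-month visit, later look-backs cannot make up for this, and the Section 12.3 recovery duty is a loose substitute. Neither Section 12.3 nor Section 13.5.6 names the primary endpoint event as something to ask about.

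Two stronger statements should not be made. The first is that survivorship is biased upward: the direction depends on absence being related to failure, and the illustrative bounds of 71.8% and 87.3% lie on both sides of 85.0%. The second is that this rule accounts for the whole range: the documents give no rate of non-COVID missed visits or of successful recovery, so neither the effect of the rule nor the gain from changing it can be calculated. The bounds show only that unknown outcomes at the planned level of loss could matter. The change is worth making because it is cheap and protects the primary endpoint.

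**What to change.** - Remove the restriction at the end of Section 13.5.6, so that mailed VAS, ASES and VR-12 forms and at least three documented contact attempts apply to every missed visit, whatever the reason. Keep recording the missed visit as a deviation.
- Add an explicit item to the contact: any reoperation, revision or device removal on the study shoulder since last contact, and its date.
- In Section 12.3, allow a subject to be classed as lost to follow-up only after these attempts have failed.
- For Visit 4, continue to seek dated reoperation status after the window closes, since it can be established in retrospect.

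The cost is protocol wording, one added question, and a few calls or mailings per missed visit, including some after the Visit 4 window. Some questionnaires would be completed by mail instead of in clinic, which the plan already accepts for COVID-19. Range of motion would still be missing for these visits.

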14. SAFETY

14.1 Safety Variables

Safety will primarily be assessed through frequency and incidence of adverse events..

15. EFFECTIVENESS

15.1 Effectiveness Variables

15.1.1 Primary

The primary endpoint of this study is survivorship (lack of reoperation/device removal) at 12 months postoperative.

15.1.2 Secondary

The secondary endpoints of this study are:

- Implant survivorship at visit intervals other than 12 months
- VR-12 scores at 3 months, 6 months, and 12 months postoperative
- ASES rating scale at 3 months, 6 months, and 12 months postoperative
- VAS pain scores at 3 months, 6 months, and 12 months postoperative
- Range of motion (ROM) at 3 months, 6 months, and 12 months postoperative

The above endpoints based on continuous data will be reported as both raw and change from baseline (CFB) results.

16. STATISTICAL ANALYSIS AND PLANNED ANALYSIS

16.1 Introduction

This study is a post-marketing, single treatment group, prospective study conducted at up to three study centers. The study will be conducted at as many as ten (10) centers in the U.S. Subjects will be enrolled in the trial for a period of 12 months. The objectives of the statistical analyses are to evaluate safety and effectiveness of the BioWick SureLock implant in the reattachment of soft tissue to bone in rotator cuff repairs.

A study center is defined as a hospital or medical office under the control and supervision of the Principal Investigator.

16.2 Sample Size and Power

The study is sized with respect to the primary one-year survivorship endpoint of the study. Assuming an observed one-year survivorship of 85%, a total of 59 subjects is required in order to estimate the true survivorship within a 95% confidence interval with a half-width precision of 10.7%. This assumes a two-sided $\alpha=0.05$ level of significance and that the data come from a binomial distribution. In order to account for a 15% lost-to-follow-up rate, the sample size will be upwardly adjusted to 71 total subjects.

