Exclusion Criteria	
 1. Clinical diagnosis of a rotator cuff tear of the subscapularis that requires repair (not including debridement); 2. Conditions which, in the opinion of the Principal Investigator, may limit the subject's ability or willingness to follow post-operative care or study instructions; 3. If female, subject is pregnant; 4. Presence of local or systemic infection; 5. Suprascapular nerve compression requiring release or documented by EMG-NCV; 6. Substance abuse, including tobacco, alcohol, or illicit drugs which, in the investigator's judgment, could impair healing or influence study compliance; 7. Foreign body sensitivity. If material sensitivity is suspected, testing should be completed prior to device implantation; 8. Insufficient blood supply or previous infection which may hinder the healing process; 9. Subject conditions including: insufficient quantity or quality of bone or soft tissue, or immature bone where the device may impact or disrupt the growth plate; 10. Subject is a prisoner or member of another vulnerable population; 11. Cortisone injection within 6 weeks prior to surgical treatment; 12. Use of immune suppressants or chemotherapeutic medications within the last 12 months;

	13. Use of systemic corticosteroids at any daily dose for more than 1 month within the last 12 months.
Safety Evaluation	Safety evaluations will be based on the frequency and incidence of device related adverse events.
Planned Sample Size	A maximum of 71 subjects will be enrolled in the study.

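### Section 16.2: 59 subjects at 85% survivorship do not give a 10.7% half-width; the figure fits 50 subjects, so the 15% loss allowance appears to be applied twice on the way to 71

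*Combined protocol and SAP*

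**What the plan says.** All the inputs are in section 16.2 (Sample Size and Power). The starting value is given by "Assuming an observed one-year survivorship of 85"%. From it the section concludes that "59 subjects is required in order to estimate the true survivorship within a 95% confidence interval with a half-width precision of 10.7"%, at a two-sided 5% level and on the assumption that "the data come from a binomial distribution". It then adds the loss allowance: "In order to account for a 15% lost-to-follow-up rate, the sample size will be upwardly adjusted to 71 total subjects".

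The synopsis (section 6) carries the result forward as a cap: "A maximum of 71 subjects will be enrolled in the study". Neither place names the method for the confidence interval, mentions any number of subjects other than 59 and 71, or says that 59 already contains an allowance for loss.

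**The concern.** The textbook half-width for a proportion of 85% with 59 subjects is about 9%, so 10.7% looks wrong on sight. It also comes close to the exact binomial figure for a smaller number, 50, which gives 59 when inflated once for 15% loss. That suggests an evaluable number and an enrolled number were confused, and the same allowance then used again.

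The study has one arm, no comparator, no hypothesis and no performance goal. The precision statement is therefore the whole justification for the enrolment. Section 16.5.1 makes the one-year estimate and its 95% interval the primary result, so readers will compare the achieved interval with the planned one. As written they cannot tell which of two designs was meant:

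- a target of 10.7%, which needs about 50 evaluable and 59 enrolled by the exact method; or
- a target a little under 10%, with 59 or 60 evaluable and 70 or 71 enrolled.

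The two differ by up to 12 subjects (71 − 59).

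**Working it through.** **Inputs** (all from section 16.2): survivorship p = 0.85; n = 59; 95% two-sided, so z = 1.96; stated half-width 0.107; loss 15%; total 71. The model is binomial and the interval method is not named, so several were tried.

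**1. The plan's own figure: half-width at p = 0.85, n = 59**

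- Wald: 1.96 × √(0.85 × 0.15 / 59) = 0.0911.
- Wald with continuity correction: 0.0911 + 1/(2 × 59) = 0.0911 + 0.0085 = 0.0996.
- Exact (Clopper-Pearson), with 0.85 × 59 = 50.15 survivors interpolated: limits 0.733 and 0.930, half the total width = 0.0983. With whole counts it is 0.0989 at 50/59 and 0.0947 at 51/59.

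| Other methods | Half-width |
|---|---|
| Wilson | 0.0908 |
| Wilson with continuity correction | 0.0988 |
| Agresti-Coull | 0.0932 |
| Jeffreys | 0.0902 |
| Log-log, no censoring | 0.0946 |

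The range is 9.0% to 10.0%, and 10.7% is not reproduced. The excess is 10.7 − 9.96 = 0.7 points at the least and 10.7 − 9.02 = 1.7 points at the most. Rounding cannot explain it, because the plan gives one decimal.

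Changing the confidence level does not help: a one-sided 5% limit gives 7.65% and a 99% interval gives 11.97%. Solving the Wald formula for p at n = 59 and 0.107 gives p ≈ 0.77, not 0.85. The one n = 59 quantity that comes close is the lower arm of the Jeffreys interval (0.1069), but an arm is not a half-width.

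**2. The n that does give 10.7% at p = 0.85**

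- Wald: 1.96² × 0.1275 / 0.107² = 42.8, so 43.
- Exact: 0.1072 at n = 50 and 0.1061 at n = 51.
- Wilson with continuity correction: 0.1067 at n = 51.
- Wald with continuity correction: 0.1067 at n = 52.

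None of these is 59.

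**3. The loss allowance, n / (1 − 0.15)**

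- 50 / 0.85 = 58.8, so 59: the number printed as required.
- 59 / 0.85 = 69.4, so 70, not 71.
- 59 × 1.15 = 67.9, so 68, not 71.
- 60 / 0.85 = 70.6, so 71.
- 59 × 1.20 = 70.8, so 71.
- Loss implied by going from 59 to 71: 1 − 59/71 = 16.9%.

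One unstated input, 50 subjects with an exact interval, thus explains both 10.7% and 59. The step from 59 to 71 is one subject more than the stated 15% gives.

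**4. What 71 enrolled would deliver**

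71 × 0.85 = 60.35, so about 60 evaluable. At 85% (51/60) the half-width is 0.0903 (Wald) or 0.0974 (exact). The exact lower arm is 0.1157, so the lower limit is 0.85 − 0.1157 = 0.734.

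**The case against.** The double allowance is an inference. The plan never mentions 50, and the match to 50 holds only for the exact interval; Wald points to 43 and the continuity-corrected Wald to 52. It also needs 42.5 survivors out of 50, while the achievable counts give 10.97% (42/50) and 10.46% (43/50). A strict limit of 10.70% would need 51, and 51/0.85 = 60. A second allowance applied to 59 gives 70, so the explanation does not reach 71, and a 20% uplift would. All of this stands, and it is why the cause can only be said to appear so. It does not touch the arithmetic error, which remains whatever its cause.

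The error is also conservative. At 59 or 71 subjects every method listed gives a narrower interval than stated, 71 is only a maximum, and no test or threshold depends on 10.7%. That is correct and limits the consequence to a misstated rationale, but it does not make the statement true.

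Finally, section 16.5.1 plans a Kaplan-Meier estimate with censoring, while section 16.6 calls for complete cases, so a binomial half-width only approximates the primary interval. This does not rescue the figure, because section 16.2 chooses the binomial model itself, and the log-log interval without censoring gives 9.5% at n = 59. It does bear on the fix: the method named in 16.2 should agree with the one used in 16.5.1.

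**Conclusion.** The concern holds. It is an error to correct, not a flaw that threatens the trial.

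- **Firm:** at 85% survivorship and n = 59, no standard two-sided 95% interval has a half-width of 10.7%. The correct value is 9.1% (Wald) or 9.8% (exact), within 9.0% to 10.0% across the methods tried.
- **Firm:** 59 is not the number required for 10.7%. That needs 43 evaluable (Wald) or 50 to 51 (exact), which is 51 or 59 to 60 enrolled after one 15% allowance, not 71.
- **Firm but small:** 59 with 15% loss gives 70, not 71.
- **Probable only:** the 15% allowance was applied twice. This rests on the exact interval and on rounding 58.8 up to 59.

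The study is not undersized for its stated target. Either it is more precise than it claims, or its enrolment exceeds what its own criterion needs.

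**What to change.** Rewrite the paragraph in section 16.2. Name the interval method, make it consistent with the one-year interval in section 16.5.1, and show the evaluable and the enrolled numbers as separate steps. If enrolment stays as it is, the text could read:

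> With 71 enrolled and 15% lost to follow-up, about 60 subjects are evaluable. At an observed survivorship of 85%, the exact 95% confidence interval has a half-width of about 9.7% and a lower limit of about 73%.

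If 10.7% really is the target, state the chain as about 50 evaluable and 59 enrolled under the exact method, and give the reason for enrolling up to 71. If 59 is meant as the evaluable number, the half-width is about 9.8% (exact) or 9.1% (Wald), and a 15% allowance gives 70 enrolled. If a Kaplan-Meier interval is to be the reference, name its transformation and quote the precision for that interval.

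The cost is one paragraph. No subjects are added, and the first option leaves the synopsis maximum unchanged.
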